Eligible participants will be scheduled for an fMRI and/or EEG session to assess and measure the ability to self-activate reward-related regions. The fMRI session will be conducted at either the Duke-UNC Brain Imaging and Analysis Center (BIAC) and/or the UNC Biomedical Research Imaging Center (BRIC), where we have secured a contract for neuroimaging data acquisition. Female participants will have a urine pregnancy test prior to fMRI scanning; the test will be verified to be negative in order to proceed with the scanning session. The EEG sessions will take place in private testing space in the Levine Science Research Center or the BIAC. The real-time neurofeedback visit will be scheduled within 60 days of the screening visit. We are using this window to allow for limited availability of the MRI scanner as well as flexibility to find an ideal time for the participant (e.g., evening or morning scan time). MRI participants may fill out a screening form confirming they are still eligible to be scanned or review a completed screening form if filled out at the screening visit. A carbon monoxide breath test may also be conducted but will not be used in determining eligibility.

Participants may complete some or all of the following tasks: Reward Activation Task, Passive Viewing Task, and Reward Learning Task. All of these tasks aim to assess how adults can learn to interact with neurofeedback provided from an fMRI or EEG system. The tasks vary slightly from each other in terms of stimuli used (personalized pictures, images provided by the experimenters, feedback display, etc.). It may be possible that we will not be able to get a good EEG or fMRI signal for some participants, based on equipment error or head size. If this occurs, participants will be debriefed and paid for their time. We will be sure to emphasize there was no error on the participant's part, and that sometimes the signal is difficult to acquire for a variety of reasons.

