Some participants may feel uncomfortable or confined once positioned within the bore of the MRI system. This potential reaction is reduced by discussing the procedure prior to entry into the magnet room, by providing the participant with a panic button that they can use to immediately signal the experimenter and the MR technician, and by frequently communicating with the participant over the intercom during the scan session. In addition, participants may be placed into a practice mock scanner prior to the regular scanning session, in order to determine if they will be comfortable in the MRI. This mock scanner consists of a decommissioned GE scanner bore without active RF gradients. This facility is located adjacent to the research scanners at the BIAC. Nevertheless, if participants continue to feel uncomfortable, the imaging procedure is terminated and the participant is removed from the magnet. Special protections will also be implemented to prevent claustrophobia or panic attacks during the neuroimaging session. A contingency plan has been established by [name] and her team and is designed to minimize anxiety. The procedure is detailed below:

Experimenter: I'd like to ask you some questions to see how you're feeling right now. On a scale of 1 to 10, where 1 is no anxiety, and 10 is the most anxiety you have ever felt, how anxious do you feel right now?

Anxiety Rating: _____

If the Anxiety rating is 7 or higher: Do you feel like you are in control of your anxiety right now, or do you feel like you may lose control of your anxiety?

In control? YES | NO

If the anxiety rating is 7 or higher AND the participant reports feeling out of control, implement Panic Protocol, below.

If the anxiety rating is 5 or higher, implement Relaxation Protocol, below.

If the anxiety rating is 4 or lower, offer the Relaxation Protocol, below.

Panic Protocol

Experimenter: Let's take a walk for a few minutes.

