If anxiety rating is still 7 or higher, do another round of 10 breaths of deep breathing and reassess anxiety. If anxiety rating has not reduced after that, escort the participant to the Duke Emergency Department.

If anxiety rating is reduced and participant is reporting an increasing sense of control over his/her anxiety, proceed to the Relaxation Protocol, below.

Relaxation Protocol

Escort the participant to a room outside the testing environment where a comfortable chair is available.

Ask the participant to sit down, and say,

I would like you to listen to this tape and follow the instructions. It will be guiding you through some relaxation exercises. It will take approximately ten minutes to complete the tape. I'll come back to check on you when you're done. Start the progressive muscle relaxation tape. When the tape is finished, assess the participant's anxiety level a final time.

Anxiety Rating: _____

In control? YES | NO

Provide professional referral resources as needed.

[name] who is psychiatrist will be on call during all scanning sessions.

Adverse Event and Serious Adverse Event reporting: Adverse events are recorded in an Adverse Event Log and reported annually to the IRB via the Continuing Renewal Process. In Accord with the IRB, AEs are considered SAEs, if they are serious, unexpected, and related to the protocol. We will report SAEs to the IRB within 1 week of occurrence.

Data Analysis & Statistical Considerations

Behavioral, EEG, and genetic data will be analyzed using statistical software including MATLAB, R, Python, and SPSS. The genetic information will be sent to the Duke University DNA Analysis Center for analysis. Imaging data will be analyzed using commercially available programs including Python, MATLAB, and FSL.

For the fMRI data, following data collection, the time series of activation within the VTA107,125 will be extracted for each participant. Primary analyses on these data will be conducted on a within and between-subject basis as follows:

To assess the ability of adults with and without ND to activate reward-related brain areas (e.g., VTA, striatum, PFC). To address this question we will extract time courses from the target areas and examine the brain response (BOLD signal) to personalized and non-personalized drug and non-drug cues.

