Only participants meeting all inclusion and no exclusion criteria will be enrolled in the study. Pre-screening for appropriateness to undergo MRI scanning will be completed prior to the procedure to make sure to exclude participants who are not safe to undergo MRI scanning such as people who have metal implants, non-removable piercings, a copper IUD, have worked with metal, or had an eye injury involving metal. Protocols are in place for participants who may experience anxiety or panic attacks during study assessments. Urine pregnancy test is required for each female prior to scanning procedure. The test must be negative in order to proceed. The PI and her study team will review appropriateness of participants for the study.

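### The Panic Protocol's last step sends every participant to the Duke Emergency Department, although fMRI may be done at the UNC BRIC and no destination is given for sessions there

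*Combined protocol and SAP*

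**What the plan says.** Under Real-Time Neurofeedback Visit, the fMRI session may be held at either or both of two centres: the "Duke-UNC Brain Imaging and Analysis Center (BIAC) and/or the UNC Biomedical Research Imaging Center (BRIC"). Of the second centre, the plan says that it is one "where we have secured a contract for neuroimaging data acquisition". EEG sessions are assigned to other space or to the BIAC, not to the BRIC, so the point concerns fMRI only.

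The Anxiety assessment procedure, in the Risk/Benefit Assessment section, sets the entry rule: "If the anxiety rating is 7 or higher AND the participant reports feeling out of control, implement Panic Protocol, below". The Panic Protocol then moves from a walk to a first round of breathing and, if needed, a second: "If anxiety rating is still 7 or higher, do another round of 10 breaths of deep breathing and reassess anxiety". Its final escalation is "If anxiety rating has not reduced after that, escort the participant to the Duke Emergency Department". The alternative branch is "If anxiety rating is reduced and participant is reporting an increasing sense of control over his/her anxiety, proceed to the Relaxation Protocol".

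One other facility is named in the procedure, the optional mock scanner: "This facility is located adjacent to the research scanners at the BIAC". Data & Safety Monitoring adds, without distinguishing sites or identifying the protocols meant, "Protocols are in place for participants who may experience anxiety or panic attacks during study assessments".

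**The concern.** This is the last safety step for someone whose panic has not settled. It tells staff to accompany the participant, so the destination has to suit the place where they are standing. UNC scanning is an option already under contract. At the BRIC, staff who follow the script would take a distressed participant to a different institution's emergency department, and staff who depart from it would have to improvise. A written contingency plan exists to avoid that choice. At stake is the handling of a rare acute event. Allocation, endpoints and analysis are not touched.

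**Working it through.** No statistical formula applies. The check sets the relevant texts side by side and follows one participant through the script.

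**Inputs**
- Permitted fMRI sites (Real-Time Neurofeedback Visit): 2, the BIAC and the UNC BRIC.
- Emergency destinations named (Panic Protocol): 1, the Duke Emergency Department.
- Other mentions: the BRIC appears only under Real-Time Neurofeedback Visit, and an emergency department appears only in the Panic Protocol. UNC destinations named: 0.
- Site branches in the anxiety, panic and relaxation scripts: 0.

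**One path through the script.** Take a participant at the BRIC who gives a rating of 9 and feels out of control.
1. Both entry conditions are met, so the Panic Protocol starts with the walk.
2. After the walk, leaving for relaxation requires both lower anxiety and no continuing loss of control. Suppose neither holds; the first ten breaths follow.
3. The rating is still 9, which is at least 7, so the second ten breaths follow.
4. The rating is still 9. The instruction is the escort to Duke.

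No step on this path depends on where the scan took place. The same text is correct for a BIAC session and misdirects a BRIC session.

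**Is the gap filled elsewhere?** The statement in Data & Safety Monitoring only says that protocols exist. The on-call psychiatrist is mentioned at the end of the Relaxation Protocol, but the Panic Protocol never tells staff to call, and on-call cover is not a destination. The mock scanner's location at the BIAC suggests that the script was written with that centre in mind. That is an inference, and the finding does not need it.

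**Size.** The plan enrols up to 150 participants and gives no UNC share, no split between fMRI and EEG, and no rate of panic. On the documents alone, the number scanned at UNC could be anything from 0 to 150. Multiplying assumed shares and rates would only return the assumptions, so no expected count is given.

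**The case against.** **Existing safeguards.** The strongest objection is that few participants will reach this step and that those who do are not left without help. Claustrophobia and an anxiety diagnosis within the past six months are exclusions, and MRI candidates are pre-screened. Participants have a panic button and intercom contact, the scan is stopped if discomfort continues, and a psychiatrist is on call for every scanning session. All of this stands, and it is why the point is minor. It lowers the chance of reaching the last step but does not correct the step's destination.

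**UNC's own arrangements.** The BRIC may have emergency procedures, and the contract may cover them. Neither is in the documents. A reader might therefore infer that UNC participants have no emergency route. The documents do not support that: a destination is named, but it is not specific to the site. What is shown is a written instruction that does not fit one permitted site and does not defer to any local procedure.

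**The trigger.** A reader might also infer that the trigger is defective, because a rating that falls from 10 to 9 has in a literal sense come down, and a participant with no growing sense of control would then meet neither branch. That reading detaches the sentence from the one before it, which sets the threshold at still 7 or higher. Read together, the natural meaning is a rating not brought below 7, and a 9 leads to the emergency department. The complaint about wording does not stand as a fault in the plan.

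**Conclusion.** The point holds in a narrow form. The final step of the Panic Protocol names one institution's emergency department for sessions that may be held at another institution's scanner, and the document offers no alternative for those sessions. It is a stated rule that misdirects if followed, so it is more than a missing detail. The severity is minor: the event is rare, several safeguards come before it, and no statistical quantity changes.

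The conclusion rests on the document text and on the UNC option being used for at least some scans. It assumes no distance between the centres, no panic rate, and nothing about UNC's local procedures. It does not extend to a claim that UNC participants lack emergency care or that the escalation threshold is wrong.

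**What to change.** In the Panic Protocol, replace the fixed Duke destination with the emergency department designated for the scanning site: Duke for BIAC sessions, and the one agreed with the UNC BRIC for sessions there. At the same step, instruct staff to contact the on-call psychiatrist.

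Leave the trigger on the anxiety rating alone. Adding a requirement that the participant also feels out of control would narrow the present rule. Someone who regains control while the rating stays at 7 or higher does not qualify for relaxation after the walk, can reach the last step, and is now escorted. The added condition would remove that escalation.

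The cost is a short protocol amendment and one confirmation with the UNC site. The analysis is unchanged.

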Reward Activation Task (ReAcT): Participants may be randomly assigned to one of two groups. One group, the Veridical Feedback Group, will receive veridical neurofeedback from a reward related region, which may include the VTA, striatum, PFC, etc., while they are inside the MRI or while wearing the EEG headset. The other group, the Noise Control Group, will receive noise feedback that they are instructed is real or yoked sham feedback that is yoked to a participant's feedback in the Veridical Feedback Group. This group will serve as a critical control condition for the experiment. All participants will be debriefed in full about the study groups, random assignment, and the purpose of each group in contributing to our understanding of the reward-related brain regions' role in reward processing in individuals with and without ND.

Participants may complete the ReAcT. The ReAcT consists of two types of runs: test runs (one pre-test and one post-test) and training runs (see Fig. 1 for a sample task design). For both groups the pre-test measures baseline reward-related brain activation prior to receiving rt-fMRI or EEG neurofeedback. For

the Veridical Feedback Group, the training runs train participants to use rt-fMRI or EEG neurofeedback to more efficiently and successfully increase their brain activity. For the Noise Control Group, the training runs serve as a control wherein they continue to try to increase brain activity. For all participants, the post-test measures if participants are better able to activate the brain after training.

Test runs: For both Groups the pre and post-test runs are identical and contain two or three trial types: Activate, Count, and Rest. During Activate trials participants will try to increase reward feelings to personalized images of rewarding items (e.g., favorite food, picture of a pet; see Fig. 1). During Count trials participants will count backwards, providing a standardized period for all participants. During Rest trials, participants are instructed to either not think of anything in particular or to view and think about an image shown to them (neutral-positive image). The test runs will have 5-7 repetitions of each trial, separated by a jittered inter-trial-interval (ITI).

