Training runs: For both Groups training runs will consist of two or three trial types: Activate, Count, and Rest. Participants will be given the same instructions as the test runs. The Activate and Rest trials will now have an interactive display, e.g., a thermometer, graph, signal bar, etc. Feedback display: For the Veridical Feedback Group, during the Activate trials the feedback display will show the average of brain activity, represented as percent signal change from baseline. The feedback display will be updated approximately every 1-10 seconds. For the Noise Control Group the feedback display will either display random values centered at 0 or yoked feedback from a participant in the Veridical Feedback Group. For both Groups, during the Rest trials, the feedback display will show random values that do not reflect brain activity. The purpose of the rest trial during the training runs will be to serve as a visual control. During Count trials, participants will view a neutral-positive cue or image (e.g., shape or picture). Each trial type will be repeated 5-7 times, separated by a jittered ITI.

Passive Viewing Task: In the passive viewing task participants will view the same images they provide for the ReAcT task. Participants with ND will also view some pictures of personalized smoking cues (e.g., cigarette of their choice). MRI participants who are not ND will not view smoking-related images. Participants will be instructed to relax and passively view the images. They will be asked to rate the images for valence (neutral to positive) and provide intermittent ratings of craving.

Reward Learning Task: In this task, participants will be asked to view various neutral or positive images (symbols/pictures/objects, e.g., white square, yellow circle). Some trials will contain the images only and some will contain the images along with a feedback display. The feedback display may vary somewhat in design and may include feedback designs such as: a thermometer, graph, growing/shrinking balloon, etc. Participants goal will be to learn to interact with the feedback display by regulating their thoughts. As part of this interaction with the feedback display, participants will rate their level of motivation prior to, during, and/or after each feedback trial.

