To evaluate whether rt-fMRI neurofeedback improves the ability to increase reward-related brain activation in individuals with and without ND. To address this question we will compare individual's BOLD response to: baseline (passive viewing of reward images), Pre-Test (view personalized and non-personalized non-drug cues prior to neurofeedback), Training (view personalized, non-drug cues while receiving neurofeedback), and Post-Test (view personalized and non-personalized non-drug cues following neurofeedback). In this manner we will characterize and quantify individual's ability to increase brain activity to personalized, non-drug rewarding stimuli.

To examine the relationship between activation of reward-related regions via neurofeedback and dopamine availability (as assessed genetically). To assess this question we will first send the genetic data to the Duke University DNA Analysis Facility for analysis. Once the SNPs and VNTRs have been analyzed we will correlate individual's level of dopaminergic related genetic material (e.g., COMT, DAT) to their ability to regulate reward-related activation during the task.

To examine the effects of neurofeedback on clinically relevant outcomes, including reward responsivity and smoking related behaviors. To assess this we will examine participants brain activity during the Passive Viewing Task and the ReAcT. We will also perform a simple Delay to Smoking Assessment where we will measure (in minutes) how long participants take to smoke their first cigarette. We will also measure how many cigarettes they smoke during their break. We will correlate individual's ability to increase brain activation to personalized, non-drug cues in the ReAcT with both their time to initiate smoking and the number of cigarettes smoked.

Data & Safety Monitoring

Summarize safety concerns, and describe the methods to monitor research subjects and their data to ensure their safety, including who will monitor the data, and the frequency of such monitoring. If a data monitoring committee will be used, describe its operation, including stopping rules and frequency of review, and if it is independent of the sponsor (per 45 CFR 46.111(a) (6)).

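### The neurofeedback aim compares display-on Training BOLD with display-off phases, and neither built-in control for the display (Rest trials, Noise Control Group) is assigned to an analysis

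*Combined protocol and SAP*

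**What the plan says.** **Analysis.** Under Data Analysis & Statistical Considerations, the second listed aim (Aim 2 below) states: "we will compare individual's BOLD response to: baseline (passive viewing of reward images), Pre-Test", followed by Training and Post-Test. The Training phase is described as "Training (view personalized, non-drug cues while receiving neurofeedback". The comparison is then given its meaning: "In this manner we will characterize and quantify individual's ability to increase brain activity to personalized, non-drug rewarding stimuli". The opening of the section says the analyses run both within and between subjects, without naming the between-subject factor.

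**Test runs** (Design & Procedures, Reward Activation Task). "For both Groups the pre and post-test runs are identical and contain two or three trial types". No feedback display is described for them. The same section gives the post-test the job of showing whether participants activate the brain better after training.

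**Training runs** (same section). "The Activate and Rest trials will now have an interactive display, e.g., a thermometer, graph, signal bar, etc". It updates about every 1-10 seconds. On Activate trials the Veridical Feedback Group sees its own brain signal, and the Noise Control Group sees either random values or another participant's yoked feedback. In both groups, "during the Rest trials, the feedback display will show random values that do not reflect brain activity", and the reason is given: "The purpose of the rest trial during the training runs will be to serve as a visual control". Count trials show a cue or image, and no display is assigned to them.

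**Trial types.** Both kinds of run may contain either two or three of Activate, Count and Rest. The text does not say which may be dropped.

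**The concern.** Training differs from the other three phases in two respects at once: participants are regulating with feedback, and they are watching a display that changes in response to something they are told is their brain. A phase comparison cannot separate the two unless a control is used. The protocol recognised this, since it gives the training Rest trials a visual-control purpose and calls the Noise Control Group critical to the experiment. The analysis section then uses neither.

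A display response in the target regions is plausible on the protocol's own account. The Background says dopamine tracks motivationally relevant information and signals departures from expected outcomes, and a gauge that participants are trying to move supplies such information.

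At stake are the Training contrasts in Aim 2. The individual ability score used in the genetic and smoking correlations is also exposed if Training data enter it. A display response equal in everyone would not alter those correlations, but one that varies between people would contaminate them.

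**Working it through.** The plan gives no effect size, SD, alpha or power for Aim 2, so there is no stated figure to reproduce. The check is algebra on the design, followed by an illustration with assumed values.

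**Terms.**
- L = true change in self-activation from Pre-Test to Training; P = the same from Pre-Test to Post-Test.
- dA, dR = BOLD response to the display alone on Activate and Rest trials in training runs. Both are zero in test runs, and the Count display term is zero throughout, because no display is described there.
- The response to Rest or Count is otherwise taken as unchanged between runs (assumption).

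**Expected value of each contrast.**

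| Scoring | Training − Pre-Test | Post-Test − Training | Post-Test − Pre-Test |
|---|---|---|---|
| Activate alone | L + dA | (P − L) − dA | P |
| Activate − Count | L + dA | (P − L) − dA | P |
| Activate − Rest | L + (dA − dR) | (P − L) − (dA − dR) | P |

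Training against passive viewing also carries dA if scored on Activate alone, since no display is described for passive viewing. Post-Test − Pre-Test contains no display term under any scoring.

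**Which scoring does the plan use?** It does not say. Aim 2 lists personalized and non-personalized cues for Pre-Test and Post-Test but only personalized cues for Training. The Stimuli section assigns personalized images to Activate and generic ones to Count and Rest. That leans towards Activate-only scoring in Training but does not settle it.

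**Between groups.** Write V for Veridical and N for Noise Control. The group difference in Training − Pre-Test is
- Activate alone: (L_V − L_N) + (dA_V − dA_N);
- Activate − Rest: (L_V − L_N) + (dA_V − dR_V) − (dA_N − dR_N).

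Either removes a display response common to both groups. For Activate − Rest the remainder need not be zero. In the Veridical group the Activate display shows brain signal and the Rest display shows random values; in a Noise participant given random values, both are random. The group difference in Post-Test − Pre-Test is P_V − P_N, with no display term.

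**Illustration of size.** Let δ be the display response divided by the SD of the paired difference. Assume no true change (L = 0), Activate-only scoring and a two-sided paired z-test at 0.05:

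P(reject) = Φ(δ√n − 1.96) + Φ(−δ√n − 1.96)

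For δ = 0.3 and n = 50: δ√n = 0.3 × 7.071 = 2.121, so Φ(0.161) + Φ(−4.081) = 0.564.

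| n | δ = 0 | 0.1 | 0.2 | 0.3 | 0.5 |
|---|---|---|---|---|---|
| 25 | 0.05 | 0.08 | 0.17 | 0.32 | 0.71 |
| 50 | 0.05 | 0.11 | 0.29 | 0.56 | 0.94 |
| 100 | 0.05 | 0.17 | 0.52 | 0.85 | >0.99 |

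The values 50 and 100 are the planned maxima without and with nicotine dependence; 25 is an arbitrary smaller subgroup. The values of δ are assumptions. If the display response cancels fully, the rate returns to the δ = 0 column.

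**The case against.** The strongest reply is that the design already handles this. The post-test is assigned the learning question and is free of the display. Calling the training Rest trials a visual control suggests that an Activate-minus-Rest contrast was intended. The Noise Control Group also sees a display, and analyses are to run between as well as within subjects. The targets are VTA, striatum and PFC rather than visual cortex, and nothing in the documents shows that a display alone drives them.

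Much of this stands. A reader might infer that the display response *will* be counted as self-activation. The documents do not support that: no contrast is defined, so the bias is conditional on the scoring. A reader might also infer that a Training rise in the Noise Control Group must be artefact. The protocol says those participants keep trying to raise their brain activity, some on feedback they are told is real, so a rise could reflect genuine effort. Nor does the plan say that a fall from Training to Post-Test would be read as failed transfer.

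What does not stand is that the controls are in use. The analysis section names no Rest trial and no Veridical-versus-Noise comparison, and Aim 2 mentions only nicotine-dependence status as a grouping. Rest may be absent from some runs altogether. Aim 2 lists Training beside the test phases with no lower standing.

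**Conclusion.** The point holds in conditional form. Aim 2 mixes display-on and display-off BOLD and leaves both available controls unassigned. Under Activate-only or Count-referenced scoring, the bias in Training minus Pre-Test is the whole display response dA; under Activate-minus-Rest it is dA − dR. The size of either is unknown, and the rejection rates above show sensitivity to assumed values, not an estimate for this trial.

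It would go too far to conclude that Aim 2 as a whole is compromised: Post-Test minus Pre-Test is clean on this issue. This rests on reading the test runs and passive viewing as free of a display, which is how they are described.

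**What to change.** In the Aim 2 analysis text:

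1. Name Post-Test minus Pre-Test, compared between the Veridical Feedback and Noise Control groups, as the learning estimate. This matches the role the task description already gives the post-test.
2. Score each Reward Activation Task run as Activate minus Rest within that run.
3. Require Rest trials in every test and training run, replacing the present option of two trial types that could leave Rest out.
4. Report Training (Activate minus Rest) as a secondary measure of on-line regulation, also compared between groups. State that the subtraction may not fully cancel the display response in the Veridical group, because its Activate and Rest displays differ in content.

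**Cost.** Items 1, 2 and 4 are wording. Item 3 is a task requirement: Rest can no longer be omitted, and a run made without it cannot be given the within-run score. The score is likely to be somewhat noisier. With equal variances σ² and correlation ρ between the Activate and Rest averages, the variance of the difference is 2σ²(1 − ρ), which exceeds σ² whenever ρ < 0.5.
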